5.0 STUDY CALENDAR

Pre-Study Testing Intervals

- To be completed \leq 16 DAYS before registration: History and physical.
- To be completed \leq 6 months before registration: Serum creatinine.

Visit week	Prior to Surgery		Day of Surgery**	Post-Surgery***			
	Prior to Registration†	Baseline*	0	6	12	18	24
Visit #	1	2		3 (A)	4 (A, B)	5 (A, B)	6
Tests and observations							
History & physical (weight, bp, pulse)	E	E		X			X
Height	X						
Serum creatinine	X						
Pregnancy test	C						
Concomitant therapies		X		X	X	X	X
Adverse events		X		X	X	X	X
Surgical adverse events				X(1)	X(1)	X(1)	X(1)
Suicidal ideation monitoring				X (2)	X (2)	X (2)	X (2)
Tobacco use assessment (Appdx IX)	X	X	X	X	X	X	X
Surgical team message		X					
NCI Smoking Quitline		X (3)		X (3)	X (3)		
Sample submission							
Salivary Cotinine Measure		X	X	X	D	D	X
Patient questionnaires							
Contemplation Ladder (Apdx III)	X			X	X		X
SEQ-12 (Apdx IV)		X		X	X		X
FTND (Apdx V)		X					
PHQ-9 (Apdx VI)	X (4)			X	X		X
LASA-12 (Apdx VII)		X			X		X
Was It Worth It Survey (Apdx VIII)					X		X
Drug and Behavioral Support Adherence Logs (Apdx X)		X		X	X		
Correlative study (optional)							
Whole blood	To be collected at baseline, see Sections 6.2 and 14.0.						

† Pre-study testing may be performed on the same day as the baseline visit (see also, Section 7.1).

* Baseline: After randomization and at the time the surgical message is discussed with the cancer patient. If performed within 7 days prior to baseline, the Tobacco Use Assessment need not be repeated.

** Surgery must occur after the TQD defined at baseline and can be performed no sooner than 10 days after randomization and no more than twelve weeks after randomization.

*** Post surgery visits can be +/- 14 days

A Patient-completed booklets for Weeks 12 and 18 should be given to patients at the Week 6 visit. Institutional staff should telephone patients within one week prior to Weeks 12 and 18 to remind them that they will either be completing these booklets by telephone at Weeks 12 and 18 or that they may bring the completed booklet to the clinic when they provide saliva samples for cotinine measurements (see Footnote D).

B May be done by telephone or in person (see footnote D).

C For women of childbearing potential. Must be done within 7 days prior to registration/randomization.

D Patients will be asked to come to the treating institution to provide saliva samples for cotinine measurement. A physician visit is not required.

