7.3 Target Quit Date

Following the baseline visit, patients will receive the full 12 week supply of drug. The target quit date (TQD) is to be determined during the baseline visit and should occur prior to the planned date of surgery. It must be at least 10 days after randomization. While it is understood that it is rare for surgery in this patient population to be delayed, in order to allow for flexibility in exigent circumstances, the maximum time from randomization to the TQD will be 12 weeks.

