7.4 Pharmacologic Intervention (Varenicline)

The initiation of the one-week dose escalation period of varenicline/placebo treatment will be considered Day 1 and the target quit date (one week later) will thus be Day 8 of therapy. Patients will be provided with instructions on the proper use of the medication (i.e., time of day to take the medication).

During Week 1, the dosing will be one of the 0.5 mg varenicline/placebo pills per day for the first 3 days followed by two 0.5 mg pills a day (morning and evening) for the next 4 days.

Weeks 2-12: Day 8 is the target quit day and on this day the patient will take two 0.5 mg pills twice daily (morning and evening). Patients will stay on this dose for 11 weeks.

Agent	Dose	Route	Day	
Varenicline/Placebo	0.5 mg	Oral	Days 1-3	1 pill per day
Varenicline/Placebo	0.5 mg	Oral	Days 4-7	1 pill twice per day – Minimum of 8 hours apart
Varenicline/Placebo	0.5 mg	Oral	Days 8-84	2 pills twice per day – Minimum of 8 hours apart (4 pills per day total)

Dosing should occur with 240 mL of water and it is recommended that patients eat prior to dosing to decrease gastric upset. It is recommended that there be at least 8 hours between the morning and evening dosing. If a dose is missed, the patient should take it as soon as s/he remembers. If it is almost time for the next dose (within 6 hours), the patient should skip the missed dose and take the next one as scheduled. Patients should not take a double dose of varenicline/placebo.

Participating institutions should have a suicide ideation monitoring and response procedures in place. An example of such procedures has been provided in Appendix XI.

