8.2 Dose Modifications

The following general guidelines apply to all adverse events except suicidal ideation or personality change (see Sections 8.2.7 and 8.2.8). Additional information regarding insomnia and nausea is provided in Sections 8.2.5 and 8.2.6.

- All missed doses should be considered as skipped and not delayed. That is, the duration of treatment must not continue past the original 12-week stop date.
- Patients may be re-challenged only one time for grade 3 events. That is, if a particular adverse event recurs after a dose reduction and rechallenge, varenicline/placebo will be permanently discontinued.
- If treatment is skipped for more than four weeks due to toxicity, permanently discontinue varenicline/placebo.

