8.2.7 Suicidal ideation: Varenicline is known to cause suicidal ideation, patients must be screened for suicidal ideation at Weeks 6, 12, 18, and 24. If a patient responds with a positive (1+) response to question 9 on the PHQ9, s/he will be evaluated by a physician using the CTCAE.

Any patient with CTCAE grade 2 or higher suicidal ideation will immediately discontinue treatment with varenicline/placebo and be referred to a mental health professional in accordance with institutional guidelines. For reference, the CTCAE grades 1 through 4 for suicidal ideation are provided below:

Grade 1: Increased thoughts of death but no wish to kill oneself

Grade 2: Suicidal ideation with no specific plan or intent

Grade 3: Specific plan to commit suicide without serious intent to die which may not require hospitalization

Grade 4: Specific plan to commit suicide with serious intent to die which requires hospitalization

8.2.8 Personality Change: Any patient with CTCAE grade 3 or greater personality change will discontinue treatment with varenicline/placebo and be referred to a mental health professional in accordance with institutional guidelines. For reference, the CTCAE grades 1 through 4 for personality change are provided below:

Grade 1: Mild personality change

Grade 2: Moderate personality change

Grade 3: Severe personality change; hospitalization not indicated

Grade 4: Life-threatening consequences, threats of harm to self or others; hospitalization indicated

8.2.9 Somnambulism: Any patient experiencing sleep walking will discontinue treatment with varenicline.

8.2.10 Pregnancy: Varenicline/placebo will be immediately permanently discontinued for any patient who becomes pregnant during the treatment period of the study.

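### Suicidality screens run on the surgery clock and dosing on the drug clock, so no scheduled screen is due before drug Day 51; one telephone screen during dosing would cheaply narrow the gap

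*Combined protocol and SAP*

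**What the plan says.** Section 8.2.7 states that "Varenicline is known to cause suicidal ideation" and that "patients must be screened for suicidal ideation at Weeks 6, 12, 18, and 24". A positive answer to PHQ-9 item 9 leads to physician grading. Grade 2 or higher means immediate discontinuation and referral to a mental health professional.

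The Section 5.0 calendar places suicidal ideation monitoring only in the post-surgery columns and adds that "Post surgery visits can be +/- 14 days". Section 9.1 solicits suicidal ideation and personality change at baseline and at the same four post-surgery weeks.

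Dosing follows a different clock. Section 7.4 says "The initiation of the one-week dose escalation period of varenicline/placebo treatment will be considered Day 1", puts the target quit date on Day 8 and ends maintenance dosing on Day 84. Under Section 8.2, "the duration of treatment must not continue past the original 12-week stop date". The calendar links the two clocks: "Surgery must occur after the TQD defined at baseline and can be performed no sooner than 10 days after randomization", with an upper limit of twelve weeks. Section 7.3 says of the target quit date: "It must be at least 10 days after randomization".

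The earlier checks (item 9 before registration, solicited events at baseline) come before dosing, because Section 7.3 supplies drug after the baseline visit. The day-of-surgery column holds only the tobacco assessment and saliva.

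**The concern.** A scheduled screen can trigger the stopping rule in 8.2.7 only while the patient is taking drug. If the screens mostly fall late in dosing or after it, the rule has little or no scheduled trigger, although referral still works at every visit.

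There is also a reporting consequence. Section 13.1.1 promises safety data summaries, but nothing says whether suicidality assessments will be shown as on-drug or off-drug. A table that pools them could present largely post-treatment screening as evidence about the treatment period.

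The plan gives no reason for this timing. Section 13.4 describes 12 weeks after surgery as the end of treatment, yet the last planned dose falls at least 9 days before that date (Day 84 against Day 93 or later). This suggests that the two clocks were conflated.

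**Working it through.** **Plan's own anchors.** First dose is Day 1, so the target quit date is 1 + 7 = Day 8. Twelve weeks is 12 × 7 = Day 84. Days 8-84 are 77 days, or 11 weeks, which agrees with Section 7.4.

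**Range of surgery day S on the drug clock.**
- Earliest: the day after the target quit date, so S = 9.
- Latest: the target quit date is at least 10 days after randomization, so first dose is at least 10 − 7 = 3 days after it. Surgery is at most 84 days after randomization, so S = 84 − 3 + 1 = 82.

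**Week 6 screen.** It is due on drug day S + 42. Dosing days before it are S + 41. Dosing days left, counting the screen day, are 84 − (S + 42) + 1. With the visit 14 days early, the screen is on S + 28 and the dosing days before it are S + 27.

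The documents give no distribution of time to surgery, so the surgery days below are illustrative assumptions.

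| Surgery on drug day | Days after target quit date | Week 6 due on drug day | Dosing days before screen (of 84) | Dosing days left | Dosing days before screen if visit is 14 days early |
|---|---|---|---|---|---|
| 9 | 1 | 51 | 50 (60%) | 34 | 36 (43%) |
| 22 | 14 | 64 | 63 (75%) | 21 | 49 (58%) |
| 36 | 28 | 78 | 77 (92%) | 7 | 63 (75%) |
| 42 | 34 | 84 | 83 (99%) | 1 | 69 (82%) |

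In the first row, 43 of the 50 dosing days before the screen (Days 8-50) are at full dose. The earliest permitted Week 6 visit is 9 + 28 = Day 37.

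**When Week 6 is on drug.** S + 42 ≤ 84 gives S ≤ 42 on nominal dates. The limit is S ≤ 56 for a visit 14 days early and S ≤ 28 for one 14 days late. At S = 82, Week 6 is Day 124, which is 40 days after the last dose.

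**Later screens.**
- Week 12: S + 84, so Day 93 at the earliest. Fourteen days early, S + 70 ≤ 84 requires S ≤ 14.
- Week 18: 9 + 126 − 14 = Day 121 at the earliest.
- Week 24: 9 + 168 − 14 = Day 163 at the earliest.

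**Effect of one telephone screen on Days 15-21.** The initial unscreened stretch becomes 14-20 dosing days. After the call, a patient with Day 9 surgery waits another 51 − 21 = 30 to 51 − 15 = 36 days for Week 6. A patient operated on after Day 42 has 84 − 21 = 63 to 84 − 15 = 69 dosing days remaining with no further nominal screen. One call narrows the gap but does not close it.

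**The case against.** The strongest reply is that the risk is small and already covered.

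- **Risk.** Section 9.1 notes that the boxed warning was removed in December 2016. Section 10.1 summarises pooled evidence of no increase in suicidality. Eligibility excludes patients with a positive item 9 answer or active untreated psychiatric illness. Nothing in the documents shows that ideation starts early in dosing. This limits the expected benefit, but the protocol still mandates the screen and the stopping rule, so the timing should let them work.
- **Other routes.** Sections 7.4, 9.1, 9.2 and 10.1 provide for site procedures, neuropsychiatric monitoring, adverse-event reporting, and instructions to patients and families. These stand. They are unscheduled or depend on self-report, and the model policy in Appendix XII acts once a patient reports ideation. The DSMP cited in Section 10.1, the consent form, the patient information sheets and the wallet card were not available and may add detail.
- **Prompt surgery.** Section 7.3 says "it is rare for surgery in this patient population to be delayed", so many patients may have one on-drug screen at Week 6. That also stands, but even surgery on Day 9 puts it at Day 51.
- **A simpler remedy.** Item 9 could be asked at the existing day-of-surgery contact, which comes earlier than a week-3 call when surgery is prompt. This is a reasonable complement. It comes late when surgery is late, and it misses patients who never have surgery.
- **Existing time rules.** Section 9.2 splits adverse-event forms at 30 days after last treatment, and Section 9.1 has a 7-day rule for attributing depression. Neither produces an on-drug or off-drug summary of suicidality.

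**Conclusion.** The concern holds as a cheap improvement. On nominal dates no scheduled post-baseline suicidality screen is due before drug Day 51, when 60% of dosing is over; with the full early allowance the limit is Day 37, or 43%. A patient operated on after drug Day 42 has no nominal on-drug screen.

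These limits assume the planned 84 days of dosing and a target quit date on Day 8. How many patients fall at each point is unknown, because the plan gives no time-to-surgery distribution.

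A further group is affected. Section 12.2.2 lets patients who never have surgery complete the drug, yet they have no surgery date from which to time a screen. Section 13.6 allows for up to 20% not reaching surgery, or 783 − 626 = 157 patients; how many would stay on drug is not stated.

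**What to change.** 1. Add one scheduled telephone contact timed from first dose, at a point chosen by the sponsor's clinicians (for example within the first few weeks). Ask PHQ-9 item 9 and the two solicited events, in person if the patient is in hospital. Keep every post-surgery screen. Patients still awaiting surgery, or who never have it, should receive the call too.
2. In the safety summaries, use recorded dose dates to classify solicited events and item 9 answers as on-drug or off-drug by arm. Item 9 looks back 2 weeks (Appendix VI), so show answers given within 14 days after the last dose as a separate row. Report by arm how many patients had at least one on-drug assessment.
3. The safety population in Section 13.1.1 requires surgery. List screens from dosed patients who had no surgery separately so that they are not lost.

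The cost is one short contact per patient, one calendar column, matching text in 8.2.7 and 9.1, and one split in the safety tables. Calendar footnote B already allows the Week 12 and 18 visits by telephone, Section 8.2.3 allows telephone toxicity checks, and daily dosing is logged (Section 11.1.8, Appendix X). The downsides are site time and physician follow-up of positive item 9 answers, some of them unrelated to drug.

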8.3 Unblinding Procedures

Unblinding can be done only in cases of an emergency. Follow the directions below to unblind patient treatment. Please note that if a treatment assignment is unblinded, the patient must discontinue protocol therapy.

Emergency Unblinding Procedures:

Examples of emergencies include 1) a life-threatening unexpected adverse event that is at least possibly related to the investigational agent and for which unblinding would influence treatment decisions; or 2) medication error, such as accidental overdose. Expected adverse events are listed in the “Toxicities” section below.

Contact the Alliance Executive Officer on call by calling [REDACTED], pressing 1 to speak with an operator, and then asking for [name] to return the call.

The institution must provide the following information to the Alliance Executive Officer:

- Alliance study ID (i.e., “A211401”)
- Alliance patient ID number (e.g., “999999”)
- Patient initials (e.g., “L, FM”)
- Institution name
- Name and telephone number of treating physician
- Name and contact information of person requesting the unblinding procedure
- Name and contact information of person to inform of treatment assignment
- Reason for emergency unblinding

Please remember that an emergency unblinding request may be authorized only by an Alliance Executive Officer, and emergency unblinding applies only if unblinding would influence management of the medical situation.

After the Executive Officer deems unblinding is warranted, the treatment assignment will be provided to the contact person at the treating site.

9.0 ADVERSE EVENTS

The prompt reporting of adverse events is the responsibility of each investigator engaged in clinical research, as required by Federal Regulations. Adverse events must be described and graded using the terminology and grading categories defined in the NCI’s Common Terminology Criteria for Adverse Events (CTCAE), Version 4.0. The CTCAE is available at [REDACTED] Attribution to protocol treatment for each adverse event must be determined by the investigator and reported on the required forms. Please refer the NCI Guidelines: Adverse Event Reporting Requirements for further details on AE reporting procedures.

9.1 Routine adverse event reporting

Adverse event data collection and reporting, which are required as part of every clinical trial are done to ensure the safety of patients enrolled in the studies as well as those who will enroll in future studies using similar agents. Adverse events are reported in a routine manner at scheduled times according to the study calendar in Section 5.0. For this trial, Adverse Event: Baseline, Adverse Event: Solicited and Adverse Event: Other are used for routine AE reporting in Rave.

Attribution of Depression: When reporting depression, the following guidelines should be used for determining attribution to varenicline/placebo:

- If depression existed before the patient started drug, and the severity has not changed, then the event should not be reported as at least possibly related to varenicline/placebo.
- If depression started or worsened after the patient started drug (regardless of smoking status), the event should be reported as at least possibly related to varenicline/placebo.
- If depression starts 7 days or more following cessation of drug, then the event should not be reported as related to varenicline/placebo. because the half-life of the drug is less than 7 days.

Solicited Adverse Events: The following adverse events are considered "expected" and their presence/absence should be solicited, and severity graded, at baseline and at 6, 12, 18 and 24 weeks after surgery.

CTCAE v4.0 Term	CTCAE v4.0 System Organ Class (SOC)
Personality change*	Psychiatric disorders
Suicidal ideation*	Psychiatric disorders

- * Although the black box warning in the prescribing information has been removed (in December, 2016), patients will be monitored for neuropsychiatric events including hostility or changes in behavior or thinking that are not typical for the patient, or for suicidal ideation or suicidal behavior. See Sections 8.2.7 and 8.2.8.

Collection of surgical adverse events: For the purpose of determining the primary endpoint of the study, the following surgical adverse events **must be** collected at 24 weeks after surgery.


 • 30-day mortality • 30-day re-hospitalization • 1-year mortality • Anastomotic failure • Anesthesia-related respiratory complications • Bleeding (transfusions > 5 U) • Coma (> 24 hours) • Deep venous thrombosis/ thrombophlebitis • Failure to wean from the ventilator • ICU readmission • Impaired bone healing • Implant loss (breast reconstruction) 	
 • Increased postoperative pain • Renal insufficiency/failure • Return to operating room • Sepsis/septic shock • Stroke/cerebral accident • Surgical infection (organ space) • Surgical site infections • Urinary tract infections • Increased postoperative surgical stay • Increased scarring and asymmetry • Intubation (unplanned)/re-intubation • Lower rates of successful digital replantation (microsurgery) 	
 • Myocardial infarction • Pneumonia • Prolonged intubation • Prolonged ventilator support • Pulmonary complications • Pulmonary embolism • Reduced skin flap survival • Vascular complications • Vein graft failure • Venous thromboembolism • Ventilator (> 48 hours) • Wound healing (delayed) • Wound infection (sternal) • Wound infections (superficial and deep)
---	--	--

9.2 CTCAE Routine Reporting Requirements

In addition to the solicited adverse events listed in Section 9.1, the following table outlines the combinations of time points, grades and attributions of AEs that require routine reporting to the Alliance Statistics and Data Center. Questions about routine reporting should be directed to the Data Manager.

Combinations of CTCAE Grade & Attribution Required for Routine AE Data Submission on Case Report Forms (CRFs)

Attribution	Grade 1	Grade 2	Grade 3	Grade 4	Grade 5
Unrelated			a	a	a
Unlikely			a	a	a
Possible		a	a, b	a, b	a, b
Probable		a	a, b	a, b	a, b
Definite		a	a, b	a, b	a, b

- a) Adverse Events: Other CRF - Applies to AEs occurring between registration and within 30 days of the patient's last treatment date, or as part of the Clinical Follow-Up Phase.
- b) Adverse Events: Late CRF - Applies to AEs occurring greater than 30 days after the patient's last treatment date.

9.3 Expedited Adverse Event Reporting (CTEP-AERS)

Investigators are required by Federal Regulations to report serious adverse events as defined in the table below. Alliance investigators are required to notify the Investigational Drug Branch (IDB), the Alliance Central Protocol Operations Program, the Study Chair, and their Institutional Review Board if a patient has a reportable serious adverse event. The descriptions and grading scales found in the NCI Common Terminology Criteria for Adverse Events (CTCAE) version 5 will be utilized for AE reporting. The CTCAE is identified and located on the CTEP website at:

 All appropriate treatment areas should have access to a copy of the CTCAE. All reactions determined to be "reportable" in an expedited manner must be reported using the Cancer Therapy Evaluation Program Adverse Event Reporting System (CTEP-AERS).

For further information on the NCI requirements for SAE reporting, please refer to the 'NCI Guidelines for Investigators: Adverse Event Reporting Requirements' document published by the NCI.

Note: A death on study requires both routine and expedited reporting regardless of causality. Attribution to treatment or other cause must be provided.

9.3.1 Expedited Reporting Requirements for Adverse Events that Occur on Studies under an IND/IDE \leq 30 Days of the Last Administration of the Investigational Agent/Intervention^{1,2}

FDA REPORTING REQUIREMENTS FOR SERIOUS ADVERSE EVENTS (21 CFR Part 312)

NOTE: Investigators **MUST** immediately report to the sponsor (NCI) **ANY** Serious Adverse Events, whether or not they are considered related to the investigational agent(s)/intervention (21 CFR 312.64)

An adverse event is considered serious if it results in **ANY** of the following outcomes:

- 1) Death
- 2) A life-threatening adverse event
- 3) An adverse event that results in inpatient hospitalization or prolongation of existing hospitalization for \geq 24 hours
- 4) A persistent or significant incapacity or substantial disruption of the ability to conduct normal life functions
- 5) A congenital anomaly/birth defect.
- 6) Important Medical Events (IME) that may not result in death, be life threatening, or require hospitalization may be considered serious when, based upon medical judgment, they may jeopardize the patient or subject and may require medical or surgical intervention to prevent one of the outcomes listed in this definition. (FDA, 21 CFR 312.32; ICH E2A and ICH E6).

ALL SERIOUS adverse events that meet the above criteria **MUST** be immediately reported to the NCI via CTEP-AERS within the timeframes detailed in the table below.

Hospitalization	Grade 1 Timeframes	Grade 2 Timeframes	Grade 3 Timeframes	Grade 4 & 5 Timeframes
Resulting in Hospitalization \geq 24 hrs	10 Calendar Days			24-Hour; 5 Calendar Days
Not resulting in Hospitalization \geq 24 hrs	Not required		10 Calendar Days	

NOTE: Protocol specific exceptions to expedited reporting of serious adverse events are found in the Specific Protocol Exceptions to Expedited Reporting (SPEER) portion of the CAEPR

Expedited AE reporting timelines are defined as:

- “24-Hour; 5 Calendar Days” - The AE must initially be reported via CTEP-AERS \leq 24 hours of learning of the AE, followed by a complete expedited report \leq 5 calendar days of the initial 24-hour report.
- “10 Calendar Days” - A complete expedited report on the AE must be submitted \leq 10 calendar days of learning of the AE.

¹ Serious adverse events that occur more than 30 days after the last administration of investigational agent/intervention and have an attribution of possible, probable, or definite require reporting as follows:

Expedited 24-hour notification followed by complete report \leq 5 calendar days for:

- All Grade 4, and Grade 5 AEs

Expedited 10 calendar day reports for:

- Grade 2 adverse events resulting in hospitalization or prolongation of hospitalization
- Grade 3 adverse events

- Expedited AE reporting timelines defined:
 - “24 hours; 5 calendar days” – The investigator must initially report the AE via CTEP-AERS ≤ 24 hours of learning of the event followed by a complete CTEP-AERS report ≤ 5 calendar days of the initial 24-hour report.
 - “10 calendar days” - A complete CTEP-AERS report on the AE must be submitted ≤ 10 calendar days of the investigator learning of the event.
- Any medical event equivalent to CTCAE grade 3, 4, or 5 that precipitates hospitalization (or prolongation of existing hospitalization) must be reported regardless of attribution and designation as expected or unexpected with the exception of any events identified as protocol-specific expedited adverse event reporting exclusions (see below).
- Any event that results in persistent or significant disabilities/incapacities, congenital anomalies, or birth defects must be reported via CTEP-AERS if the event occurs following treatment with an agent under a CTEP IND.
- Use the NCI protocol number and the protocol-specific patient ID provided during trial registration on all reports.

Additional Instructions or Exclusions to CTEP-AERS Expedited Reporting Requirements for Phase 2 and 3 Trials Utilizing an Agent Under a CTEP IND or non-CTEP IND:

- All adverse events reported via CTEP-AERS (i.e., serious adverse events) should also be forwarded to your local IRB.
- Grade 3/4 hematosuppression and hospitalization resulting from such do not require CTEP-AERS, but should be submitted as part of study results. All other grade 3, 4, or 5 adverse events that precipitate hospitalization or prolong an existing hospitalization must be reported via CTEP-AERS.
- All new malignancies must be reported via CTEP-AERS whether or not they are thought to be related to either previous or current treatment. All new malignancies should be reported, i.e. solid tumors (including non-melanoma skin malignancies), hematologic malignancies, myelodysplastic syndrome/acute myelogenous leukemia, and in situ tumors. In CTCAE version 4.0, the new malignancies (both second and secondary) may be reported as one of the following: (1) Leukemia secondary to oncology chemotherapy, (2) Myelodysplastic syndrome, (3) Treatment-related secondary malignancy, or (4) Neoplasms benign, malignant and unspecified-other. Whenever possible, the CTEP-AERS reports for new malignancies should include tumor pathology, history or prior tumors, prior treatment/current treatment including duration, any associated risk factors or evidence regarding how long the new malignancy may have been present, when and how the new malignancy was detected, molecular characterization or cytogenetics of the original tumor (if available) and of any new tumor, and new malignancy treatment and outcome, if available.
- Treatment expected adverse events include those listed in Section 10.0 and in the package insert.
- CTEP-AERS reports should be submitted electronically.
- Pregnancy loss is defined in CTCAE as “Death in utero.” Any Pregnancy loss should be reported expeditiously, as Grade 4 “Pregnancy loss” under the Pregnancy, puerperium and perinatal conditions SOC. A Pregnancy loss should NOT be reported as a Grade 5 event under the Pregnancy, puerperium and perinatal conditions SOC, as currently CTEP-AERS recognizes this event as a patient death.
- A neonatal death should be reported expeditiously as Grade 4, “Death neonatal” under the General disorders and administration SOC.

